This project involves obtaining peripheral blood mononuclear cells (PBMCs) and colorectal tissue samples from study participants to measure adenylate kinase 2 (AK2) and muscle-type creatine kinase (CKM) enzyme levels in an “older adult” group (65-80) when compared to a “younger adult” group (18-50). Both AK2 and CKM has been demonstrated to be vital enzymes in converting the prodrug tenofovir (TFV) into its active form, tenofovir diphosphate (TFV-DP).¹⁻⁴ However, no study has yet investigated the effect of aging on AK2 or CKM in colorectal tissues relevant to HIV infection and prevention. This study will investigate the AK2 and CKM variability in individuals from the younger and older age groups in preparation for a follow-up study investigating how the pharmacokinetics (PK) of tenofovir (TFV) vary with altering levels of cellular enzymes in different age populations. A finding of clinically significant differences in the activity of AK2 or CKM, may indicate the need for dose adjustment of TFV for HIV treatment or prevention depending upon age to either reduce toxicity or enhance efficacy.

In this study, individuals who are interested in participating will be screened for eligibility. If eligible, participants will return for a single study visit. At the study visit, blood will be drawn and colorectal tissue will be obtained via flexible sigmoidoscopy. Participants can participate in an optional PK sub-study if they are already taking a tenofovir (TFV)-based regimen for prevention or are willing to take a daily TFV-based regimen for 7 days prior to the flexible sigmoidoscopy. Subsequently, AK2 and CKM will be analyzed in PBMCs and colorectal tissue using mass spectrometry.

II. INTRODUCTION

The prevalence of HIV in older adults (≥ 50 years of age) living with HIV has increased, in part to the success of antiretroviral therapy extending life expectancy, with nearly half of the people living with HIV (PLWH) in the United States over the age of 50, and 16% ≥ 65 years of age (data from the Centers for Disease Control and Prevention). However, each year, there are nearly 40,000 new HIV diagnosis infections in the United States and 1.7 million infections globally.^{5,6} Individuals over the age of 50 account for 17% of new HIV diagnoses annually. In 2020, men accounted for 80% of new HIV diagnosis in the United States, with nearly 70% in gay, bisexual, or other men who reported male-to-male sexual contact. With this in mind, there is a need to develop and optimize efficacious strategies for prevention of HIV infection in this population⁵.

The recent development of pre-exposure prophylaxis (PrEP) for the prevention of HIV can significantly decrease the risk of HIV infection with proper adherence.⁷ Tenofovir is a prodrug that is the main antiviral component of current PrEP regimens.⁸⁻¹⁰ TFV is from the drug class known as nucleotide reverse transcriptase inhibitors (NRTIs) in which chain termination occurs during DNA synthesis by HIV reverse transcriptase, therefore, suppressing HIV replication. However, only the diphosphate form of tenofovir (TFV-DP), generated by phosphorylation of TFV by intracellular kinases, is capable of inhibiting HIV replication.

In key tissues related to HIV acquisition, it has been found that adenylate kinases and creatine kinases play a significant role in TFV activation.¹ Specifically, in colorectal tissue, it has been found that adenylate kinase 2 (AK2) is the primary kinase in the initial phosphorylation of TFV to tenofovir monophosphate (TFV-MP). Moreover, muscle-type creatine kinase (CKM) has been demonstrated to be the enzyme that is vital for the second phosphorylation, transforming TFV-MP to TFV-DP.

Previous studies have found that age has an effect on CKM expression, post-translational modifications, and activity in multiple tissues.¹¹⁻¹⁶ Thus, it is hypothesized that expression levels and post translational modifications of AK2 and CKM may differ depending upon age, therefore, altering the amount of active TFV-DP and increasing variability of protection. Therefore, it is imperative to investigate expression and post translational modifications of AK2 and CKM in colorectal tissue and PBMCs from various age populations to see if these cellular enzymes change with increasing age.

III. RATIONALE

While PrEP has been shown to be highly effective in reducing the risk of HIV infection, despite adherence to PrEP, some individuals become infected with HIV. To gain an understanding of CKM phosphorylation activity and examine whether CKM might also contribute to variability of TFV-DP activation in colonic CD4+ cells in the presence of HIV infection, we will also measure levels of CKM and TFV-DP in colonic CD4+ T cells of younger and older individuals infected with HIV taking tenofovir-based HIV treatment, as well as those taking tenofovir-based PrEP who are not infected with HIV.

This study is designed to investigate the intracellular AK2 and CKM enzymes in both colorectal tissue and PBMCs in a younger and older adult population. It is hypothesized that age alters expression and post translational modifications and expression of AK2 and CKM in colorectal tissue and PBMCs causing variability in TFV-DP levels in individuals taking tenofovir-based medications.

To test this hypothesis, colorectal biopsies and PBMCs will be collected to assess for changes in AK2 and CKM levels using mass spectrometry and changes in enzymatic activity to phosphorylate TFV from the following populations:

Cohort A: 10 younger (age 18-50) and 10 older (age 65-80) adults who are not infected with HIV and not taking tenofovir-based PrEP ("Control Cohort").

Cohort B: 10 younger (age 18-50) and 10 older (age 65-80) adults who are not infected with HIV, but are taking a TFV-based regimen (either on daily TFV- based PrEP or agree to take a daily TFV-based regimen 7 days prior to procedure). ("PrEP Cohort")

Cohort C: 10 younger (age 18-50) and 10 older (age 65-80) adults who are infected with HIV, taking a TFV-based regimen. ("ARV Cohort")

Study Objectives:

Objective	Endpoint
1. Determine if levels and activity of AK2 and CKM in colorectal tissue differ between (a) younger adults (age range 18-50 years), and older adults (age range 65-80) or	
 • Proteomics will be used to measure intracellular protein levels and modification status of kinases that phosphorylate TFV. • In individuals taking a TFV-containing regimen, colorectal tissue TFV-DP will be measured at steady-state.

(b) between HIV negative and HIV positive persons.
	
 In individuals not taking a TFV-based regimen, in vitro incubation of TFV with colorectal tissue biopsies will be performed to measure TFV activation as a function of age.

2. Determine if levels and activity of AK2 and CKM in PBMCs differ between:
 
(a) younger adults, defined as 18-50 years of age, and older adults, defined as 65-80 years of age or
 
(b) HIV negative and HIV positive persons..
	
 Proteomics will be used to measure intracellular protein levels and modification status of kinases that phosphorylate TFV. In individuals not taking a TFV-based regimen, in vitro incubations of TFV with PBMCs will be performed to measure TFV activation as a function of age. In individuals taking a TFV-containing regimen, colorectal tissue TFV-DP will be measured at steady-state.

IV. STUDY DESIGN

Overview

The design of the study will be a two-visit study, including a screening visit (Visit 1) and a sampling visit (Visit 2). During the screening visit, the individual will be assessed for eligibility. For participants scheduled for sigmoidoscopy or colonoscopy for a medical indication, the screening visit may be conducted by phone prior to the procedure. If eligible, the participant will return for the study visit ≤ 42 days following the screening visit. During the study visit, approximately 100 mL of blood will be drawn for PBMC isolation. Following the blood draw, participants will undergo endoscopic evaluation in which 10 colorectal biopsy samples will be obtained between 10-20 cm from the anal verge. Thirty adults from each age population (younger and older) will be enrolled for this study. Three cohorts (each including young and old groups) will be defined by TFV administration and HIV status.

Study Population

Three cohorts of participants will be recruited, with 10 younger and 10 older in each cohort.

Cohort A: Healthy Volunteers, not taking TFV based PrEP (Control Cohort)

Cohort B: Healthy volunteers, steady state TFV-based regimen (either on daily TFV- based PrEP or taking daily TFV-based regimen 7 days prior to procedure) (PrEP Cohort)

Cohort C: Persons infected with HIV taking TFV/FTC-based HIV treatment (ARV Cohort)

Inclusion Criteria

Participants who meet the following criteria are eligible for inclusion in this research:

1. English speaking male or female volunteers between the ages of 18-50 for younger adults or 65-80 for older adults
2. Willing to provide written informed consent
3. Willing to abstain from insertion of anything in rectum for 72 hours before and 72 hours after the endoscopic procedure for colorectal tissue collection.
4. Not currently participating in other research studies involving drugs and/or medical devices.

For participants not infected with HIV (Control Cohort A)

1. No known risk for HIV exposure or a documented negative HIV-1/HIV-2 Ag/Ab test in the past 3 months (HIV risk, but not on PrEP)
2. Documented negative HBsAg in those taking study TFV (i.e. cohort B)

For participants not infected with HIV, but taking or willing to take TFV (PrEP Cohort B)

1. Currently taking TFV-based oral PrEP daily or willing to take oral TFV-containing PrEP for one week
2. Documented negative HIV-1/HIV-2 Ag/Ab test in the past 3 months
3. Documented negative HBsAg

For participants infected with HIV (ARV Cohort C)

1. Virologically suppressed HIV for at least 6 months prior to screening.
2. Taking tenofovir disoproxil fumarate or tenofovir alafenamide containing regimen to treat HIV

Exclusion Criteria

Participants who meet any of the following criteria at screening will be excluded from the study:

1. History of inflammatory bowel disease or active inflammatory condition of the GI tract
2. History of significant gastrointestinal bleeding
3. Current medically-indicated use of warfarin or heparin or other anticoagulant medications associated with increased risk for bleeding following mucosal biopsy (e.g., daily high dose aspirin [>81 mg], non-steroidal anti-inflammatory drugs [NSAIDs], or Pradaxa®)
4. Use of systemic immunomodulatory medications within 4 weeks of enrollment
5. Use of rectally administered medications within 4 weeks of enrollment
6. Use of product containing nonoxynol-9 within 4 weeks of enrollment
7. Use of any investigational products within 4 weeks of enrollment
8. Any other clinical condition or prior therapy that, in the opinion of the investigator, would make the participant unsuitable for the study or unable to comply with the study requirements. Such conditions may include, but are not limited to, current or recent history of

severe, progressive, or uncontrolled renal, hepatic, hematological, gastrointestinal, endocrine, pulmonary, neurological, or cerebral disease.

9. Active rectal infection (GC, Chlamydia, HSV). Participants screening positive for GC/CT at the time of endoscopy will be excluded from analysis (and replaced).

For participants not undergoing a concurrent endoscopic procedure for indication unrelated to this study:

10. Hct <36%
11. Platelet count <150/mm³

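### Objective 2 concerns PBMCs, but its endpoint for participants on TFV is measured in colorectal tissue, so PBMC enzyme activity is unspecified in Cohorts B and C and cannot be compared by HIV status

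*Combined protocol and SAP*

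**What the plan says.** Section III, Study Objectives table. Objective 2 reads "Determine if levels and activity of AK2 and CKM in PBMCs differ between" (a) younger and older adults or (b) HIV-negative and HIV-positive persons. It has three endpoints:

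- proteomics for kinase protein levels and modification status, with no cohort limit;
- for people not on a TFV regimen, "in vitro incubations of TFV with PBMCs will be performed to measure TFV activation as a function of age";
- for people on a TFV regimen, "In individuals taking a TFV-containing regimen, colorectal tissue TFV-DP will be measured at steady-state".

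The third line also appears, word for word, under Objective 1, which concerns colorectal tissue.

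Section III, Rationale, is broader. Biopsies and PBMCs are both to be collected to assess enzyme levels and "changes in enzymatic activity to phosphorylate TFV from the following populations", and Cohorts A, B and C are then listed. The hypothesis concerns "AK2 and CKM in colorectal tissue and PBMCs causing variability in TFV-DP levels in individuals taking tenofovir-based medications". The same section adds a measurement of "levels of CKM and TFV-DP in colonic CD4+ T cells".

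Section IV, Overview, states that "approximately 100 mL of blood will be drawn for PBMC isolation". Table 2 and Appendix I list the PBMC draw without limiting it to a cohort.

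**The concern.** A colorectal measurement cannot answer a question about enzyme activity in PBMCs. In the Objective 2 column the in vitro line was adapted from colorectal biopsies to PBMCs, but the TFV-DP line was not. This looks like a copied line, although the documents do not confirm it.

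Every HIV-positive participant is in Cohort C and takes TFV. If the laboratory follows the endpoint as written, no PBMC activity data exist for anyone with HIV, and the activity comparison in Objective 2(b) cannot be made. The in vivo comparison of PBMC activity by age among TFV takers is lost as well. There is a single sampling visit, so cells not set aside for the assay may not be recoverable later.

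**Working it through.** **Inputs.** Section III gives three cohorts of 10 younger and 10 older adults: A (HIV negative, no TFV), B (HIV negative, on TFV) and C (HIV positive, on TFV).

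**Reproducing the plan's enrolment figure.** 3 cohorts x 10 = 30 per age group, which matches section IV, Overview. The total is 2 x 30 = 60. TFV takers are B + C = 20 + 20 = 40.

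**Does any specified measurement supply PBMC activity in TFV takers?**

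| Measurement | Where stated | Who | PBMC activity? |
|---|---|---|---|
| Proteomics | Objective 2, first endpoint | No cohort limit (60) | No: levels and modification status |
| In vitro TFV incubation with PBMCs | Objective 2, second endpoint | Not on TFV: Cohort A (20) | Yes |
| Colorectal tissue TFV-DP | Objectives 1 and 2 | On TFV: B and C (40) | No: wrong tissue |
| TFV-DP in colonic CD4+ T cells | III. Rationale | TFV takers, with and without HIV | No: colonic cells |
| TFV PK | Table 2 | HIV-uninfected TFV takers | No: plasma |
| Blood for TFV | Appendix I | PrEP or ARV cohort, per its footnote | No: PBMCs and TFV-DP not named |

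TFV-DP is named as a measurement three times (once in the Rationale, twice in the objectives table), and never in PBMCs. Section IX describes only the comparison of protein levels between age groups and adds no PBMC activity outcome.

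**PBMC activity data as written.**

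- All participants: 20 of 60 (Cohort A only).
- TFV takers: 0 of 40.
- HIV positive: 0 of 20.
- By age, Objective 2(a): 10 v 10, in vitro, Cohort A.
- By HIV status, Objective 2(b): no HIV-positive arm.

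**If the third endpoint named PBMC TFV-DP.**

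- By age among TFV takers: (10 B + 10 C) v (10 B + 10 C) = 20 v 20, or 10 v 10 within each cohort.
- By HIV status: B 20 v C 20.
- Participants with some PBMC activity measure: 20 in vitro + 40 in vivo = 60 of 60.

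The power statement in section IX plays no part here: an empty arm cannot be estimated at any sample size.

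**The case against.** The strongest reply is that this is a copying slip and not a design failure. The Rationale states the intent for all three cohorts, blood for PBMCs is drawn from everyone, and a sensible team would read the line as PBMC TFV-DP. The slip is probable. But no other section names the assay or allocates cells to it, so the error sits in the only text that defines the endpoint.

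Second, the Rationale gives a general purpose and names no PBMC assay for TFV takers, and its hypothesis does not say in which matrix TFV-DP varies. That is correct. The conflict is therefore between a stated purpose covering all cohorts and an endpoint list that does not deliver it.

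Third, proteomics still covers PBMCs in all 60 participants, including modification status, which is part of the hypothesis. This stands and limits the damage. It does not fill the gap, because the plan treats enzyme levels and enzymatic activity as separate targets.

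Fourth, the planned test in section IX concerns protein levels by age, so most of the described PBMC analysis survives. That is also true, but activity by HIV status remains part of a numbered objective.

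Fifth, PBMC TFV-DP in B v C would be an imperfect measure of enzyme activity. Both TDF and TAF are allowed, and Cohort B may mix established PrEP users with seven-day starters, so TFV-DP would also reflect drug exposure. This limits what the correction can deliver and calls for careful reporting. It does not justify leaving the arm empty.

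**Conclusion.** The point holds: the third Objective 2 endpoint is wrong as written and must be corrected. Followed literally, it leaves 40 of 60 participants without a specified PBMC activity measurement and makes the activity part of Objective 2(b) unanswerable, with 0 of 20 HIV-positive participants contributing. The protein-level and modification part of Objective 2, and the 10 v 10 in vitro age comparison in Cohort A, are intact.

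The counts assume full enrolment at the stated cohort sizes and a literal reading of the endpoint. That PBMC TFV-DP was intended is an inference from the Rationale and the duplicated line; only the sponsor can confirm it.

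**What to change.** Ask the sponsor to confirm intent and to reconcile the Rationale with the Study Objectives table.

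**If PBMC activity in TFV takers is intended:**

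- Replace colorectal tissue TFV-DP with PBMC TFV-DP at steady state in the third Objective 2 endpoint, and keep colorectal TFV-DP under Objective 1.
- State in Table 2 and Appendix I that PBMCs from Cohorts B and C are allocated to this assay.
- Report B v C with prodrug (TDF or TAF) and time on TFV shown, and say that differences in TFV-DP reflect exposure as well as enzyme activity.

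The cost is a wording change and one added assay on blood already drawn, with no extra visit or procedure. This assumes that the roughly 100 mL draw yields enough cells for both proteomics and TFV-DP; the documents give neither yield nor allocation.

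**If it is not intended:** restrict the activity part of Objective 2 to the age comparison in Cohort A, and remove activity from Objective 2(b). This costs wording only, but gives up any statement about PBMC activity by HIV status.

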12. INR > 1.2

Study Procedures

Note: This protocol requires colorectal biopsies to support the primary objectives. These are collected using an endoscope (e.g., flexible sigmoidoscope or colonoscope). We plan to use a flexible sigmoidoscope as the least invasive method to achieve our objectives. If, however, the research participant already has a colonoscopy scheduled for a medically indicated purpose, e.g., a preventive colon cancer screening, then we will coordinate with the clinical endoscopy team to obtain the biopsies by this method, in order to reduce the number of procedures related to our study. The protocol indicates some minor differences in procedures to accommodate this option.

This section includes information on visit specific study procedures. This study includes two visits, a screening visit and a sampling visit. The breakdown of the procedures on each day are as follows:

Visit 1: Screening Visit

Prescreening via email or a phone call will take place with potential participants. Those interested in the study can request that the informed consent documents be emailed or mailed to them prior to the Screening Visit.

Written informed consent will be obtained from study participants prior to any study procedures taking place. To obtain informed consent, an interactive question and answer process will occur in which the potential subject will be asked specific questions to determine their understanding of the purpose, procedures, risks and benefits of participating in the study. If, in the judgment of the investigator, the subject cannot demonstrate sufficient understanding, then that subject will be excluded from participation in the protocol. If participants do not meet the eligibility criteria, screening will be discontinued once ineligibility is determined.

The following list of activities will be completed during the screening visit:

Table 1: Visit 1 - Screening

Component	Procedure/Analysis
Administrative	
 • Obtain written informed consent • Assign participant ID (PTID) • Assess eligibility • Obtain demographic and locator information • Provide counseling: 
 • HIV/STI risk reduction counseling • HIV pre- and post- test counseling, if indicated • Provide a copy of pre- and post- visit reminders • Participants not undergoing screening colonoscopy will be provided with a Enema and directions for use prior to Sampling Visit.
Clinical	
 • Obtain complete medical history, documenting pre-existing conditions • Review and record concomitant medications • Obtain vital signs – blood pressure (BP), heart rate (HR), height, and weight (height may be obtained from EMR, and weight captured in the EMR within 6 months of screening may be obtained from EMR 
Note: Medical history and physical examination data may be extracted from electronic medical record, or performed at the time the participant presents for an endoscopic procedure scheduled for clinical indication.

Safety Labs and STI Screening (for participants not undergoing a concurrent endoscopy procedure only):	
 • Perform general physical exam • Collect rectal swab for GC/CT • Collect blood specimens for: 
 ○ Complete blood count (CBC) with differential¹ ○ AST, ALT, BUN, Creatinine¹ ○ HIV testing² ○ Syphilis testing³
PrEP cohort only for those not already on TFV-based PrEP prior to screening	
 • HBsAg (result from prior test within 12 months acceptable) • Dispense F/TDF or F/TAF for daily dosing to begin 7 days prior to study procedure (PrEP Cohort B only, not already on PrEP) • Commence daily virtual DOT for 7 days prior to study procedure

¹ Screening laboratory values are valid up to 42 days.

²See Appendix II: HIV Testing Algorithm; HIV testing not to be done in participants known to be infected with HIV

³Syphilis Chemiluminescence assay (with confirmatory RPR; FTA-ABS performed on RPR negative samples)

Visit 2: Sampling Visit (\leq 42 days since Screening Visit)

Note: Where applicable, Visit 2 may be combined with Visit 1

After eligibility is confirmed, participants will be contacted to schedule the study visit (Visit 2). Where possible, Study Visit 2 may be coordinated with a scheduled clinical procedure, such as a screening colonoscopy.

The following activities will take place at the Study Visit:

Table 2: Visit 2 – Sampling Visit

Component	Procedure/Analysis
Administrative	
 Confirm participant understood and signed informed consent Review/update locator information Confirm eligibility Provide counseling: 
 HIV/STI risk reduction counseling Provide a copy of pre- and post- visit reminders
Clinical	
 Review/update medical history Review/update concomitant medications Perform symptom-directed physical exam as needed Obtain vital signs – blood pressure (BP), heart rate (HR), Obtain 10 colorectal biopsies via flexible sigmoidoscopy or during clinically-indicated study procedure
STI Screening (For participants undergoing a concurrent endoscopy for clinical indications):	
 Collect rectal swab for CT/GC testing
Blood for PBMC Collection	
 Pre-endoscopic Procedure
TFV PK (only in HIV uninfected participants taking TFV)	
 Blood plasma

V. RECRUITMENT AND OUTREACH

Sources of recruitment will be as follows:

- Referral from treating clinicians at any regional clinic
- Prior Hopkins/Affiliates study participants who have given informed consent to be reached for future studies
- Individuals who learn about the study through advertisements or peer/network recruiting

Approved recruitment flyers will be distributed throughout the community. In addition, approved messages for social media platforms, internet recruitment and department website will be used. Staff will also follow-up with all persons who express an interest in the study in a timely manner.

VI. COMPENSATION TO SUBJECTS

Participants will be compensated for their time and inconvenience related to participation in this study. Compensation will be \$425 for completion of the study and is based upon the schedule established for DDU studies.

VII. COSTS TO SUBJECTS

There will be no costs to the subjects outside of costs to travel to the study site.

VIII. PROTECTION OF HUMAN RESEARCH PARTICIPANTS

Risks

Flexible Sigmoidoscopy: Endoscopy is uncomfortable for some persons and poses only a very small risk of perforation and bleeding when biopsies are taken. The most common adverse events associated with endoscopy are gas, bloating, and cramping which usually resolve within hours of the procedure. Taking the biopsies causes no discomfort due to the insensate epithelial lining of the colon. Pinch biopsies may cause minor bleeding which stops on its own. More significant and rare adverse events can include prolonged bleeding and/or perforation.

Participants will be screened and excluded if taking any blood thinners or have conditions that may prolong bleeding. Risk of perforation, which is a medical emergency that may require surgery, will be minimized by enrolling participants who do not have significant bowel disease and having the procedure performed by a credentialed endoscopist. Where possible, the endoscopic procedure will be paired with a procedure that may have a clinical indication, such as screening colonoscopy for colon cancer. In this case, the only additional risk to the participant are the risks of collecting pinch biopsies, which are lower in risk than the endoscopy itself..

Phlebotomy is performed by drawing blood from a vein in the forearm or antecubital fossa. This may cause pain during the insertion of the needle or slight bruising afterward.

TFV (administered as part of this research protocol): TFV disoproxil fumarate (TDF) and TFV alafenamide (TAF) are both TFV prodrugs licensed by FDA for the prevention and treatment of HIV. TFV-based PrEP regimens currently approved include emtricitabine / tenofovir alafenamide (F/TAF) or emtricitabine / tenofovir disoproxil fumarate (F/TDF). Both combination regimens are well tolerated. Risks of TFV include acute exacerbation of hepatitis B virus Immune Reconstitution Syndrome; New or worsening renal impairment; lactic acidosis; hepatomegaly with steatosis; lower bone mineral density; diarrhea; nausea; headache; fatigue; abdominal pain; rash. Risks will be minimized by confirming participants do not have hepatitis B or HIV and baseline safety labs will be monitored prior to receiving study medication. TFV-naïve participants who are not already prescribed TFV-containing regimens for PrEP or treatment will take only 7 doses, which will minimize the risks associated with chronic administration.

STI testing: Participants may become embarrassed, worried, or anxious when completing their HIV-related interviews and/or receiving STI counseling. Certain positive results (Chlamydia, gonorrhea) may need to be reported to appropriate Department of Public Health Agencies. The reporting only happens if the test result is positive and is always done confidentially.

Incidental Findings: Significant clinical findings may be discovered during study procedures, which may warrant referral for medical care and further testing. If significant clinical findings are discovered during the procedure, study subjects will be referred to the proper Johns Hopkins Division for additional evaluation and treatment as necessary.

Social Risk: Although the study site will make every effort to protect participant's privacy and confidentiality, it is possible that involvement in the study could become known to others, and that social harms may result (i.e., subjects could become known as HIV-infected or at "high risk" for HIV infection) and, consequently, be treated unfairly or discriminated against by families, friends and/or communities.

Loss of confidentiality: Although every effort will be made to protect the privacy and confidentiality of all participants, it is possible that their involvement in the study could become known to others. All guidelines for the protection of Personal Health Identifiers will be followed.

Benefits

There are no direct benefits to subjects who participate in this study. However, there may be personal satisfaction in the knowledge that they are aiding in important medical research, and that the knowledge obtained from this study will advance the field of HIV prevention. Participants will be reimbursed for their time and inconvenience.

The risks to individual participants are outweighed by potential benefits to the scientific community and to society – namely, contribution to our microbicide knowledge-bank.

IX. STATISTICAL ANALYSIS

To compare protein levels between the younger adult and older adult groups, protein abundances will be averaged within age groups. Differences in protein levels will be determined by unpaired two-tailed t test using the Benjamini-Hochberg correction for multiple comparisons, with significant differences being defined as having an adjusted p-value of <0.05. Based on our previous studies of TFV phosphorylation we estimate ~80% power to detect a 1.5-fold difference between study groups using our measured outcomes and >95% power to detect a 1.75-fold difference between study groups at our sample size.

X. CONFIDENTIALITY

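### Biopsy route and bowel preparation depend on clinical scheduling that is plausibly age-related, so the unadjusted tissue age comparison may be confounded

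*Combined protocol and SAP*

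**What the plan says.** Section IV (Study Procedures) makes flexible sigmoidoscopy the planned method for everyone. The exception is a participant who "already has a colonoscopy scheduled for a medically indicated purpose, e.g., a preventive colon cancer screening"; the biopsies are then taken during that procedure. The section describes the resulting procedural differences as minor. The notes to Visit 2 and the risk text in Section VIII both say that pairing with a clinical procedure is sought where possible.

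Three things follow the route:

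- **Preparation.** Table 1 states: "Participants not undergoing screening colonoscopy will be provided with a Enema and directions for use prior to Sampling Visit". Footnote 2 of Appendix I limits the enema to participants without a concurrent endoscopy. Preparation for colonoscopy is not described.
- **Eligibility.** The haematocrit, platelet and INR exclusions apply only to participants without a concurrent clinical endoscopy.
- **Safety laboratory tests.** Apart from the rectal swab, Appendix I omits them for screening colonoscopy.

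Biopsy site does not differ by route: it is 10-20 cm from the anal verge for all.

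In Section IX, "protein abundances will be averaged within age groups" and "Differences in protein levels will be determined by unpaired two-tailed t test", with Benjamini-Hochberg correction and significance at an "adjusted p-value of <0.05". The section has no covariate, stratum or sensitivity analysis for route or preparation. Tables 1 and 2 and Appendix I do not list either as a data item.

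**The concern.** Objective 1(a) asks whether AK2 and CKM in colorectal tissue differ between adults aged 18-50 and 65-80. If clinical colonoscopy is more common in one age group, the two sets of biopsies differ in preparation and in how participants were selected, as well as in age. An unadjusted t test cannot separate these. A preparation effect on measured protein would appear as an age effect, or would offset a real one.

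The protocol's opening summary says that a clinically significant difference in enzyme activity may indicate age-dependent dose adjustment of tenofovir, so the attribution to age matters. The argument concerns tissue only. Blood for PBMCs is drawn before the endoscopic procedure, and nothing here implies that preparation affects it.

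**Working it through.** **Inputs from the documents.** 10 younger and 10 older participants per cohort, 30 and 30 overall; two-sided 0.05; "80% power to detect a 1.5-fold difference between study groups" and ">95% power to detect a 1.75-fold difference between study groups at our sample size". No SD is given.

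**Inputs that are assumptions.** Colonoscopy shares in older (pO) and younger (pY) participants; a preparation or route effect on measured protein, g, of 1.1- to 1.5-fold; pooling of the three cohorts (n = 30 per group), which Section IX does not state.

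**1. The plan's power figures.** Without an SD they cannot be reproduced directly. Solving the noncentral t for 80% power at ln 1.5 = 0.405 gives a log-scale SD of 0.551 at n = 30 per group (0.306 at n = 10). With n = 30, the noncentrality at 1.5-fold is 0.405 / (0.551 × √(2/30)) = 2.85. At 1.75-fold it is 0.560 / 0.142 = 3.93, which gives 97.2% power. The two stated figures agree with each other, and 0.551 is used below.

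**2. Spurious age ratio with no true age effect.** Ratio = g^(pO − pY).

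- 70% and 10%: 1.1^0.6 = 1.06; 1.25^0.6 = 1.14; 1.5^0.6 = 1.28.
- 30% and 10%: 1.1^0.2 = 1.02; 1.25^0.2 = 1.05; 1.5^0.2 = 1.08.

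**3. False-positive rate of the unadjusted test** (n = 30 per group, per test, before Benjamini-Hochberg). The formula column puts the bias into the noncentral t with SD 0.551. The simulation column also reflects the wider within-group spread when routes are mixed.

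| Shares, older / younger | g | Formula | Simulation |
|---|---|---|---|
| 30% / 10% | 1.1 | 5.2% | 5.2% |
| 30% / 10% | 1.25 | 6.1% | 5.7% |
| 30% / 10% | 1.5 | 8.7% | 7.4% |
| 70% / 10% | 1.1 | 6.8% | 6.8% |
| 70% / 10% | 1.25 | 15% | 15% |
| 70% / 10% | 1.5 | 39% | 36% |

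In the last row the pooled variance becomes 0.551² + ½(0.7 × 0.3 + 0.1 × 0.9) × 0.405² = 0.304 + 0.025 = 0.328, an SD of 0.573; hence 36% rather than 39%. With 10 per group and SD 0.306, the simulated rate is about 5% throughout at 30%/10%, and 7%, 13% and 30% at 70%/10%.

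Two reference cases: with g = 1 the rate is about 5% at any imbalance, and with equal shares there is no bias. Confounding by preparation needs both an imbalance and an effect.

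**4. Masking.** At 70%/10%, a true 1.5-fold age effect opposed by a 1.25-fold preparation effect appears as 1.5 / 1.25^0.6 = 1.31-fold. Power falls from 80% to about 47% by the formula.

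**5. Cost of adjusting.** SE inflation = 1/√(1 − φ²), with φ = (pO − pY) / (2√(m(1 − m))) and m the mean share.

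| Shares | m | φ | SE | Power at 1.5-fold |
|---|---|---|---|---|
| 60% / 20% | 0.40 | 0.408 | +9.5% | about 73% |
| 70% / 10% | 0.40 | 0.612 | +26% | about 60% |
| 80% / 10% | 0.45 | 0.704 | +41% | about 51% |

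At 100%/0%, age and route cannot be separated. A sigmoidoscopy-only comparison at 70%/10% leaves 30 × 0.3 = 9 older participants overall, 3 per cohort.

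**The case against.** A reader might infer that route follows age, with colonoscopy for the older group and enema plus sigmoidoscopy for the younger. The documents do not support that. Sigmoidoscopy is the default at every age, either group may use either route, no expected share is stated, and the recruitment section does not name an endoscopy clinic as a source. The age imbalance is an inference from the screening example and the age bands.

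Nor do the documents show that preparation affects AK2 or CKM. The upper end of the assumed range equals the 1.5-fold difference the study is powered for, and at 30%/10% the inflation is small. The common biopsy site removes location as a difference. Excluding inflammatory bowel conditions and significant gastrointestinal bleeding narrows the scope for indication effects. Staff must know each participant's route, because the enema, tests and swab timing depend on it.

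All of this stands, and it limits the size that can be claimed. It does not remove the exposure. The documents do not rule out an imbalance or an effect, the eligibility tests differ by route as well, and Section IX provides no way to report which situation arose. The power loss from adjustment is also real. It argues against making the adjusted model primary, but not against a sensitivity analysis.

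**Conclusion.** The plan leaves the colorectal tissue age comparison open to confounding by route, preparation or selection. That it will be confounded is not shown. Over assumed preparation effects of 1.1- to 1.5-fold with pooled n = 30 per group, the per-test false-positive rate before Benjamini-Hochberg is about 5-9% for a 30%/10% split and about 7-36% for a 70%/10% split. These are scenarios, not forecasts. They rest on an SD back-solved from the stated power, on pooling the cohorts, and on shares and effects that the documents do not give. The point is worth acting on because the remedy is cheap and affects what a tissue difference can be said to show. PBMC outcomes are outside it.

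**What to change.** - Record each participant's biopsy route and bowel preparation, and tabulate both by age group and cohort. Record preparation separately, because the documents do not describe it for colonoscopy.
- Keep the stated t test as primary. In Section IX, prespecify two sensitivity analyses for colorectal outcomes: (i) the age comparison adjusted for route, and (ii) the age comparison restricted to sigmoidoscopy/enema participants.
- State that if routes barely overlap between age groups, or if the sensitivity results disagree with the primary, a tissue difference will not be attributed to age alone.

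The cost is a short data item and a few sentences in Section IX; no clinical procedure changes. The sensitivity estimates will be less precise: the adjusted SE is about 10% to 40% larger over the 60/20 to 80/10 splits, with power at 1.5-fold of about 73% down to 51%. Within a single cohort, adjustment could rest on very few people (at 70%/10%, one younger participant with colonoscopy), and the restricted set may be small.
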